5.1.1.9 Liver Ultrasound

Hepatic peliosis, an abnormality of the hepatic vasculature, which has the potential to cause a dramatic hemorrhage, is a rare but recognized complication of XLMTM. Serial ultrasound assessments will be used to assess change in size, shape, and structure of the liver, and will be evaluated in conjunction with serum LFTs. Refer to [Section 4.6.2](#) for details related to the monitoring, diagnosis, and treatment of hepatobiliary toxicity and the role of the site hepatologist.

5.1.1.10 Cardiac Structure and Function (ECG, ECHO and Cardiac MRI)

Unlike many neuromuscular diseases, individuals with XLMTM do not exhibit cardiac muscle disease. Mice treated with rAAV8-Des-MTM1 had asymptomatic cardiac lesions detected on necropsy (in the presence of gross over expression of myotubularin) ([Section 1.2.1.3](#)). It is unknown whether a risk exists for human subjects. Cardiac structure and function will be

routinely assessed using 12-lead ECG and ECHOs. Cardiac MRI may be performed at the discretion of the investigator in conjunction with consultation with the site pediatric cardiologist. If myocarditis is observed, cardiac catheterization and endomyocardial biopsy may be needed in exceptional cases.

If troponin I and/or troponin T is elevated above the ULN of the laboratory reference range, test selection for diagnosis and management of myocarditis or asymptomatic troponin elevation is performed at the discretion of the investigator in conjunction with consultation with the site pediatric cardiologist. Key testing is discussed below. Refer to [Section 4.6.1](#) for management of ECG, ECHO, and Cardiac MRI results and the role of the site pediatric cardiologist.

- ECG: In patients with suspected myocarditis, the ECG can display a variety of non-specific abnormalities. Interpretation of ECG by the site pediatric cardiologist may be required due to the array of ECG changes that can occur with myocarditis.
- Transthoracic ECHO: ECHO is a safe, widely available, and clinically extremely useful cardiac imaging tool, particularly for the initial assessment of myocarditis. The American College of Cardiology (ACC), American Heart Association (AHA), and European Society of Cardiology (ESC) Working Group on Myocardial and Pericardial Diseases recommend that all patients with clinically suspected myocarditis should undergo an ECHO at initial presentation ([Adeboye, 2022](#)).
- Cardiac MRI: Cardiac MRI is considered the non-invasive reference standard for diagnosis of myocarditis in the absence of contraindications to MRI. Gadolinium may be used to assess for late gadolinium enhancement, a technique used for cardiac tissue characterization due to various types of myocardial injury and fibrosis. Cardiac MRI findings change depending on the phase of disease and timing of imaging. Myocardial edema is a characteristic early feature of acute myocarditis which typically improves over days to weeks and may not be detected if cardiac MRI is performed weeks to months after symptom onset. Diagnostic sensitivity is highest within 2 to 4 weeks of symptom onset; therefore, cardiac MRI should be performed quickly in patients with suspected myocarditis ([Urzuá Fresno, 2023](#)).
- Cardiac catheterization with endomyocardial biopsy in exceptional cases: Although the gold standard for diagnosis of myocarditis is endomyocardial biopsy, this procedure is usually not required for diagnosis and management. Considering this procedure's invasiveness, low sensitivity when myocardial involvement is focal, and a complication rate ranging from 1% to 15%, the pediatric cardiologist may consider the clinical presentation to be of sufficient severity to necessitate the procedure, especially in uncommon clinical scenarios such as severe heart failure, cardiogenic shock, ventricular arrhythmias, and/or when there is significant diagnostic uncertainty, aiming to ensure the requirement of the procedure ([Pilati, 2022](#)).

5.1.1.11 Respiratory Function

5.1.1.11.1 Assessment of Ventilator Requirements with Polysomnogram

Daytime polysomnograms (ie, respiratory physiology studies) will be performed at Screening and at Week 24 to assess the number of hours of ventilator support required. Daytime polysomnograms will also be performed at Week 48 only if the subject is still on ventilator at the

time of the visit. For example, if the subject has discontinued the ventilator at Week 40, the Week 48 daytime polysomnogram is not required.

At Screening, ventilatory support will be provided for approximately 3 hours while observing the subject and subsequently the ventilatory support will be removed.

At Week 24 and Week 48, ventilatory support will be provided for approximately 1 hour while observing the subject and subsequently the ventilatory support will be removed. Additionally, if a subject is already off ventilator for 1 hour or more, the 1-hour observation period will not be required.

At Screening, Week 24, and Week 48 if any of the following criteria are met following the removal of ventilatory support, the polysomnogram will be stopped and the ventilator support will be reintroduced:

- Oxygen saturation (SpO_2) < 94% on room air for at least 20 seconds
- Increased end tidal carbon dioxide ($ETCO_2$) or transcutaneous carbon dioxide (TCO_2) of 10 mmHg or 1.33 kPA for at least 20 seconds
- $ETCO_2$ or TCO_2 > 50 mmHg for at least 20 seconds
- Increased respiratory rate by 25% over baseline value

At Screening, if the subject does not reach criteria for the reintroduction of ventilation, they will remain off of the ventilator for a maximum of 4 hours.

At Week 24 and Week 48 if the subject does not reach criteria for the reintroduction of ventilation, they will remain off of the ventilator for a minimum of 6 hours plus the amount of time off at Screening. For example, if at Screening, the subject was off the ventilator for 15 minutes, the daytime polysomnogram at Week 24 should be a minimum of 6 hours and 15 minutes off the ventilator.

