5.1.1.11.2 Assessment of Time Off Ventilator

5.1.1.11.2.1 Daily Ventilator Dependence Diary

For subjects in Part 1 who have not completed the Week 24 visit and for subjects in Part 2 (including any subjects enrolled under protocol v5 and beyond), an electronic diary will be completed by the parent/LAR/caregiver to collect the type of ventilatory support and the amount of time the subject spent off of ventilatory support in a 24-hour period. The diary should be completed daily by the same parent/LAR/caregiver (whenever possible). Site staff should set up the electronic diary prior to distribution to the parent/LAR/caregiver and review the training with the parent/LAR/caregiver. The daily diary collection will begin after informed consent (or re-consent to protocol v5 or later for Part 1 subjects) and continue through Week 48. However, if after the Week 24 visit, ventilator support has been discontinued, the daily diary will no longer need to be completed. If ventilator support is resumed, the daily diary completion will resume through Week 48 or discontinuation of the ventilatory support, whichever occurs first. For

subjects in Part 1 who have already completed the Week 24 visit, a daily diary will not be completed.

5.1.1.11.2.2 Ventilator Dependence Questionnaire

A questionnaire will be completed by the parent/LAR/caregiver to collect the type of ventilatory support and the amount of time the subject spent off of ventilatory support in a 24-hour period at clinic and contact visits ([Appendix 4](#)).

For subjects in Part 1 who have already completed the Week 24 visit, the parent/LAR/caregiver will complete the ventilator dependence questionnaire at clinic and contact visits through Month 120.

For subjects in Part 1 who have not completed the Week 24 visit and for subjects in Part 2 (including any subjects enrolled under protocol v5 and beyond), the daily diary will be completed per [Section 5.1.1.11.2.1](#). After the daily diary has been stopped or the subject has completed Week 48, the parent/LAR/caregiver will complete the ventilator dependence questionnaire at clinic and contact visits through Month 120.

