5.1.1.11.3 Guidelines for Initiating Ventilator Weaning

Weaning is the process of decreasing the amount of support that the subject receives from the mechanical ventilator, so that the subject assumes a greater proportion of the ventilatory effort. The objective is to assess the probability that mechanical ventilation can be successfully discontinued.

Weaning from invasive or noninvasive ventilatory support will be conducted in collaboration with the Investigator, site pulmonologist, and the subject's local pulmonologist, if applicable. The site pulmonologist and the local pulmonologist, if applicable, will review the results from the visit, assess the subject, and determine if the subject meets the criteria outlined in [Table 1](#) to begin reduction of hours on the ventilator. Once the subject meets and maintains the criteria outlined in [Table 1](#), the site pulmonologist and the local pulmonologist, if applicable, may change the ventilator settings and reduce the prescribed number of hours at their discretion. Refer to the ASPIRO: ATX-MTM-002 Ventilator Weaning and Discontinuation Manual for recommendations on ventilator weaning. The actual number of hours of ventilatory support a subject receives daily will be recorded via the electronic ventilator dependence diary or the Ventilator Dependence Questionnaire ([Section 5.1.1.11.2.1](#)).

Table 1: Required Parameters for Initiation of Ventilator Weaning

Assessments	Parameters
Vital signs	Normal for age
Weight	Normal for age
Respiratory function tests	
Maximal inspiratory pressure (MIP)	> 50 cmH ₂ O
Maximal expiratory pressure (MEP)	> 40 cmH ₂ O
Positive end-expiratory pressure (PEEP)	≤ 5 cmH ₂ O
Oxygen saturation (SpO ₂)	> 94%
Transcutaneous CO ₂ (TCO ₂)	35-45 mmHg
End tidal CO ₂ (ETCO ₂)	35-45 mmHg
Gas exchange markers	
Serum bicarbonate	22-27 mEq/L
Clinical judgement	Consider week-to-week clinical improvements in motor milestones (rolling over, head control, sitting unassisted); vocalization; coughing; secretions, and neuromuscular function tests (CHOP INTEND)

CHOP INTEND = Children's Hospital of Philadelphia Infant Test of Neuromuscular Disorders

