4.3 Primary Endpoint Analysis

4.3.1 Definition of Endpoint(s)

The primary efficacy endpoint is change from baseline in hours of ventilation support at Week 24.

The hours of ventilation support will be based on diary data from participants for whom diary data was collected at baseline (those administered AT132 under protocol v5 and beyond, including all participants in Part 2), and by assessment of time off ventilator questionnaire for all other participants (those administered AT132 under protocol v4 and prior). Weekly scores will be the average of ventilation hours needed for at least 5 out of the 7 days leading up to and including the analysis visit day (e.g., Day 168 for Week 24). For cases where the diary or the ventilator assessment indicates that ventilator type = "None", then zero will be imputed for the number of hours on ventilator.

The days included for the average for the particular visit week are defined by $\text{avisit} = \text{"Week"} \parallel \text{strip}(\text{put}(\text{ceil}(\text{ady}/7), \text{best.}))$, where ADY = the analysis visit day of the diary entry.

If at least 5/7 days of the visit week are non-missing, then the remaining missing values will be ignored in the calculation of average ventilation hours needed. Otherwise, if <5 non-missing diary records are available for the visit week, then up to 4 missing values will be imputed by the worst score of the week (most hours on ventilator), so that at least 5 records are available for calculating the average for the week.

Baseline is defined as the average of the diary data values in the 7 days leading up to and including the day of administration of the study drug (i.e. Analysis Day – 6 through Day 1). The missing data approach described in the paragraph above will be used if <7 days of data are available at baseline. If only non-diary ventilator questionnaire data is available at baseline, the last record prior to administration of study drug will be used for the baseline value.

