4.4.2.2 Main Analytical Approach

The secondary efficacy analyses will be conducted for the FAS.

4.4.2.2.1 Time to reduction in required ventilator support to ≤ 16 hours a day (only in participants who require invasive ventilation) at Week 24

This endpoint will be summarized for low dose and the high dose groups separately in the participants who require invasive ventilation. Kaplan-Meier plots along with median (95% CI) time from the study start date to event will be provided.

The number of hours of ventilator support at each collected time point for this analysis will be taken directly from the daily diary (Protocol V5.0 and later) or by assessment of time off ventilator questionnaire (prior to Protocol V5.0). The first instance of time reduction reported as ≤ 16 hours per day will be considered an event. Participants will be censored at either Week 24 or withdrawal from study, whichever occurs first.

4.4.2.2.2 Change from baseline in Children's Hospital of Philadelphia Infant Test of Neuromuscular Disorders (CHOP INTEND) at Week 24

The change from baseline will be analyzed using the MMRM in a similar method to that used for the primary analysis of the primary efficacy endpoint, described in [Section 4.3.2](#).

Estimated change from baseline in CHOP INTEND score at Week 24 will be summarized by dose level.

In addition, the CHOP INTEND score and corresponding change from baseline at each visit will be summarized descriptively by dose level group.

The CHOP INTEND is an assessment scale that was originally designed to quantify motor abilities in infants aged 1.4 to 37.9 months, with spinal muscular atrophy type I (SMA-I) ([Glanzman, 2010](#)) and has been validated for XLMTM ([Duong, 2021](#)). The scale contains 16 questions, each of which is scored on a scale of 0 to 4, with 0 being no response/ability to perform the movement and 4 highest ability to perform the task, per CHOP INTEND item instructions.

The score used for analysis is the total sum of all 16 questions, which will range from 0 to 64. Higher score indicates better neuromuscular function. If an item is missing or scored as "Could Not Test (CNT)" then 0 will be imputed for the item score.

If a participant has 2 assessments with a total score of ≥ 56 , the CHOP INTEND will not be required for future visits.

Subject line plots of the CHOP INTEND over time will be created.

4.4.2.2.3 Change from baseline in maximal inspiratory pressure (MIP) at Week 24

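### When a child completes the Week 24 daytime polysomnogram within the diary week, the test's own hours off the ventilator count as reduced support in the primary endpoint and can produce a one-day ≤ 16-hour event

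*Protocol*

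**What the plan says.** Protocol 5.1.1.11.1 schedules a daytime polysomnogram at Screening, at Week 24, and at Week 48 for children still ventilated. Support is withdrawn under observation. If a saturation, CO₂ or respiratory-rate criterion is met, the test stops and support goes back on. For a child who meets none of them at Screening, "they will remain off of the ventilator for a maximum of 4 hours". The later rule is a floor instead of a cap: "At Week 24 and Week 48 if the subject does not reach criteria for the reintroduction of ventilation", then "they will remain off of the ventilator for a minimum of 6 hours plus the amount of time off at Screening". In the protocol's example of 15 minutes off at Screening, "the daytime polysomnogram at Week 24 should be a minimum of 6 hours and 15 minutes off the ventilator".

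Protocol 5.1.1.11.2 has the diary and the questionnaire collect "the amount of time the subject spent off of ventilatory support in a 24-hour period". Protocol 5.1.1.11.3 adds: "The actual number of hours of ventilatory support a subject receives daily will be recorded via the electronic ventilator dependence diary" (or the questionnaire).

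SAP 4.3.1 forms each weekly score of the primary endpoint from "at least 5 out of the 7 days leading up to and including the analysis visit day". For Week 24, SAP Table 11 makes that Days 162–168. Children dosed under protocol v4 or earlier are analysed from the questionnaire. For the ≤ 16-hour endpoint in invasively ventilated children, SAP 4.4.2.2.1 states: "The first instance of time reduction reported as ≤ 16 hours per day will be considered an event". Censoring is at Week 24 or withdrawal. Neither document says what to do with a polysomnogram day.

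**The concern.** The primary endpoint is meant to describe how the child's daily ventilation has changed. On a polysomnogram day, part of the time off support is imposed by the study. Nothing in the analysis rules separates those hours from ordinary weaning, and they can move the result only towards improvement.

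The effect does not cancel in the change from baseline. The Screening test takes place between Day -70 and Day -7 (Protocol 5.3.1). The baseline week is Day -6 to Day 1 in SAP 4.3.1 and Day -7 to Day -1 in SAP Table 11. At most one day could coincide, and that test allows no more than 4 hours off.

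The sensitivity analysis in SAP 4.3.3 reuses the primary data, so it would not reveal the problem. The ≤ 16-hour endpoint is the more exposed of the two because one unconfirmed daily report is enough.

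**Working it through.** **Test length.** Minimum time off is m = 6 + s hours, where s is the time off at Screening.
- The protocol's example reproduces: 6 h + 0.25 h = 6 h 15 min.
- With s from 0 to 4 h, m runs from 6 to 10 h.

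**Primary endpoint, diary children.** Let h be the usual time off that the test replaces, and n the number of diary days averaged. The weekly mean falls by (m − h)/n.
- h = 0, n = 7: 6/7 = 0.86 h to 10/7 = 1.43 h. The recorded score is 23.14 to 22.57 h; without the test day it is 24.0 h.
- h = 0, n = 5: 6/5 = 1.2 h to 10/5 = 2.0 h.
- h = 4, m = 6, n = 7: 2/7 = 0.29 h.
- Test day the only entry that week: worst-score imputation copies it, and the fall is the full 6 to 10 h.

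For scale, 0.86/13.0 = 6.6% and 1.43/13.0 = 11% of the 13.0 h effect in SAP 4.9. That effect belongs to a comparison that will no longer be made.

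**≤ 16-hour event.** Test-day ventilation is 24 − (6 + s) − other time off. It is ≤ 16 when s plus other time off is at least 2 h. Time beyond the test minimum counts in the same way.

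| Screening time off | Ventilated on test day, minimum test, no other time off | Event? |
|---|---|---|
| 0 h | 18 h | no |
| 0.25 h | 17.75 h | no |
| 2 h | 16 h | yes |
| 4 h | 14 h | yes |

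**Timing.** The visit is Day 168 ± 14 (Protocol 5.5), so Days 154–182, which is 29 days.
- In the diary week, Days 162–168: 7/29 = 24%.
- On or before Day 168, taken here as the censoring point: 15/29 = 52%.

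The percentages assume equally likely visit days. A test on the target day falls in both intervals.

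**Questionnaire children.** The form in Protocol Appendix 4 covers the past 24 hours. A recall spanning the whole test would shift by up to 6 to 10 h in a child otherwise on 24 h/day. A recall completed before the test would not shift at all.

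**The case against.** The strongest reply is that this is not pure artefact. The polysomnogram exists to assess how much support is required, and SAP 4.3.1 speaks of hours needed. A child who stays stable off support for 8 hours has shown something real. That has force as an argument about tolerance. But the protocol says actual hours are recorded. The test rule also differs by design, with a 4-hour cap at Screening and a floor of 6 hours or more at Week 24. Mixing the test into one side of a before-and-after comparison of daily use is not a fair way to credit tolerance.

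The second reply is that the effect is small and nothing is tested. SAP 2 drops hypothesis testing, a test-driven event would sit near the censoring time, and the subject line plots may show an isolated dip. This limits the harm. The plan will still report Week 24 estimates with 95% confidence intervals and a Kaplan-Meier median.

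Three stronger readings are tempting and should be resisted.
- *Every child loses at least 6 hours of support.* The floor applies only when no restart criterion is met. A child who meets one early is barely affected.
- *Completing the test is itself a ≤ 16-hour event.* Six hours off leaves 18 hours on the ventilator, and the protocol's own example leaves 17.75.
- *The questionnaire shift is 46–77% of the planning effect (6/13.0 to 10/13.0) and falls on the low-dose group.* Protocol v4 and earlier are not in the documents, so it is unknown whether those children had this test. Protocol 5.5 marks no questionnaire at Week 24, although Protocol 5.1.1.11.2.2 calls for it at clinic visits and SAP Table 9 gives it a Week 24 window. Nor is the exposure clearly one-sided: Protocol 1.4.2 cites Week 24 data from the high-dose cohort in the v5 decision, so both groups may include questionnaire children.

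**Conclusion.** The concern holds in a limited form. For a child who meets no restart criterion and is tested on Days 162–168, study-imposed time off enters the primary Week 24 mean and favours improvement. With seven diary entries, the shift is at least about 0.9 to 1.4 h in a child otherwise on 24 h/day, and less in a child already off for part of the day.

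A test on or before Day 168 can create a ≤ 16-hour event on that day alone. This needs at least 2 h off at Screening, other time off that day, or a test longer than the minimum.

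The diary and event results rest on the current text, plus the assumption that caregivers record test hours as the instructions imply. The questionnaire effect remains a possibility that the documents do not confirm. The bias is modest, but it runs in one direction and is cheap to remove, so the SAP should be changed.

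**What to change.** The changes are to the analysis only; the conduct of the test and of weaning is untouched.

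- **SAP 4.3.1:** leave calendar days with a protocol daytime polysomnogram out of the weekly mean, and do not count them as missing. A complete diary keeps six days. A child with five entries including the test day is averaged on the remaining four, without worst-score imputation.
- **SAP 4.4.2.2.1:** state that a polysomnogram day cannot by itself be the ≤ 16-hour event.
- **Questionnaire children:** flag Week 24 values dated on the polysomnogram day or the day after, and show the Week 24 summary with and without them. The form in Protocol Appendix 4 has a date but no time, so overlap with the test cannot be established exactly.
- **Week 48:** apply the same exclusion and flag to the weekly mean and questionnaire values.

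The cost is SAP wording, a merge on the polysomnogram date, one diary day lost for some children, and one extra summary.

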5.1.1.11.2 Assessment of Time Off Ventilator

5.1.1.11.2.1 Daily Ventilator Dependence Diary

For subjects in Part 1 who have not completed the Week 24 visit and for subjects in Part 2 (including any subjects enrolled under protocol v5 and beyond), an electronic diary will be completed by the parent/LAR/caregiver to collect the type of ventilatory support and the amount of time the subject spent off of ventilatory support in a 24-hour period. The diary should be completed daily by the same parent/LAR/caregiver (whenever possible). Site staff should set up the electronic diary prior to distribution to the parent/LAR/caregiver and review the training with the parent/LAR/caregiver. The daily diary collection will begin after informed consent (or re-consent to protocol v5 or later for Part 1 subjects) and continue through Week 48. However, if after the Week 24 visit, ventilator support has been discontinued, the daily diary will no longer need to be completed. If ventilator support is resumed, the daily diary completion will resume through Week 48 or discontinuation of the ventilatory support, whichever occurs first. For

subjects in Part 1 who have already completed the Week 24 visit, a daily diary will not be completed.

5.1.1.11.2.2 Ventilator Dependence Questionnaire

A questionnaire will be completed by the parent/LAR/caregiver to collect the type of ventilatory support and the amount of time the subject spent off of ventilatory support in a 24-hour period at clinic and contact visits ([Appendix 4](#)).

For subjects in Part 1 who have already completed the Week 24 visit, the parent/LAR/caregiver will complete the ventilator dependence questionnaire at clinic and contact visits through Month 120.

For subjects in Part 1 who have not completed the Week 24 visit and for subjects in Part 2 (including any subjects enrolled under protocol v5 and beyond), the daily diary will be completed per [Section 5.1.1.11.2.1](#). After the daily diary has been stopped or the subject has completed Week 48, the parent/LAR/caregiver will complete the ventilator dependence questionnaire at clinic and contact visits through Month 120.

